10 STATISTICAL ANALYSIS METHODS

10.1 Subject Disposition

All participants who provide informed consent will be accounted for in this study.

The number of participants screened, number of screening failures, and the number of participants randomized will be summarized for all screened participants per site and overall.

The following disposition and withdrawals (including reasons for intervention and study discontinuation as provided on the eCRF) will be summarized by intervention group:

- The number of participants who are randomized
 - The number of participants who are randomized and not treated
 - The number of participants who are randomized and treated
- The number of participants who completed the intervention period
- The number of participants who discontinued study intervention
- The number of participants who completed the study
- The number of participants who discontinued the study

In addition, number and percentage of participants in each analysis population, reason(s) for exclusion from each analysis population and critical and major protocol deviations will be summarized and listed for the randomized analysis population.

10.2 Demographics and Baseline Characteristics

Demographic data and other baseline characteristics will be summarized using descriptive statistics only, for the ITT, and Safety population. The denominators for percentages will be the number of participants in each intervention group with non-missing data available for the variable of interest.

Explicitly the following characteristics will be summarized:

- Age (years)
- Age groups (<65 years, ≥65 years; and 18 to <35 years, 35 to <50 years, 50 to <65 years, 65 to <75 years, ≥75 years)
- Sex (Male, female)
- Race (American Indian or Alaska Native, Asian, Black or African American, Native Hawaiian or Other Pacific Islander, White, Mixed Race, Other, Unknown)
- Ethnicity (Hispanic or Latino, Not Hispanic or Latino, Not Reported, Unknown)
- Weight (kg)
- Height (cm)
- BMI (kg/m²)
- BMI groups (<35 kg/m², ≥35 kg/m²)

BMI (kg/m²) will be calculated using the following formula:

$$BMI = \frac{weight (kg)}{height (m) \times height (m)}$$

- Presence of comorbidities factors at randomization
 - Age (<65 years, ≥65 years)
 - Presence of chronic pulmonary disease, COPD, pulmonary hypertension (Yes, No)
 - Diabetes mellitus (type 1 or type 2) requiring medication or insulin (Yes, No)
 - Hypertension, requiring at least 1 oral medication for intervention (Yes, No)
 - Immunocompromised status due to disease (Yes, No)
 - Immunocompromised status due to medication (Yes, No)
 - Chronic disease associated with high risk for severe COVID-19 (Yes, No)
 - BMI groups (<35 kg/m², ≥35 kg/m²)
- Number of days since onset of symptoms at time of randomization [continuous and categorical: original protocol (<3 days or ≥3 days); protocol amendment 1 (<6 days or ≥6 days); and across both protocol versions (<6 days or ≥6 days)]
- Number of days since onset of symptoms at time of Day 1 [continuous and categorical: (<6 days or ≥6 days), where this is calculated as date of Day 1 – date of onset of symptoms + 1.
- SARS-CoV-2 diagnostic test at Day 1 (Positive, Negative)
- Gates MRI and WHO clinical assessment status at Day 1 (applicable categories)
- Oxygen saturation at Day 1
- COVID-19 signs and symptoms, participants with at least 2 symptoms, 3 symptoms, 4 symptoms, etc. at Day 1. Categories will not be mutually exclusive (i.e., patients having at least 3 symptoms will also be summarized in the at least 2 symptoms category).
- COVID-19 signs and symptoms at Day 1: each symptom (Yes, No)
- Alcohol and non-medical illicit drugs use in the last month (Yes, No)

10.3 Treatment Compliance and Exposure

Treatment compliance and exposure will be summarized for the Safety population.

Treatment compliance information for study drug will be collected through counts of remaining tablets in the bottle at the EOT or discontinuation of study drug. Compliance is computed as the number expected to be taken at time of EOT or discontinuation of study drug minus number remained +1 (as there is an extra tablet in a bottle) relative to the number expected to be taken will be summarized. The frequency and percentage of participants in each of the following categories will be presented: <50%, ≥50% and <75%, ≥75% and <100%, and >100% by study intervention group.

Any days that participants administered a dose of study drug will be tabulated for number of days exposure to study drug. Number of days exposure will be summarized as both continuous and categorical variables by study intervention group. For categorical presentation, the frequency and percentage of participants in each of the following categories will be presented: ≤ 7 days, 8 to ≤ 14 days, 15 to ≤ 24 days.

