## **6.8. Preparation/Handling/Storage/Accountability**

Each participant will receive a bottle containing twenty-two (22) tablets of active or placebo based on the randomization. Twenty-one (21) tablets are meant for each participant's 21 days of daily dosing. One extra tablet is provided as overage.

Xarelto®, per US Commercial Package Insert, is to be stored at 25°C (77°F) or room temperature with excursions permitted to 15° to 30°C (59° to 86°F). The same conditions will apply to the placebo-equivalent. The temperature conditions will be printed on the investigational label applied on the bottle.

Documentation of receipt, dosing, and disposal of unused medication to be maintained as per study procedures.

Study medication may be dispensed by a qualified study representative, according to dispensing instructions. Study medication may also be shipped directly to the participant's home depending on evolving circumstances related to COVID-19. Instructions will be included with the drug shipment to the participants.

Date of IP dispensing and adherence to IP administration will be recorded.

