## **7. Discontinuation/Withdrawal Criteria and Study Completion**

### **7.1. Discontinuation of Study Intervention**

Study intervention will be discontinued for the following reasons:

- Hospitalization, if the in-patient provider decides continuation of study treatment is contraindicated.
- Requirement for prohibited concomitant medications or other contraindication to study product
- Occurrence of an AE requiring discontinuation of study intervention (i.e., severe hypersensitivity, major bleeding or clinically relevant non-major bleeding)
- Request by participant to terminate study intervention
- Clinical reasons believed to be life-threatening by the physician, even if not addressed in this protocol
- Pregnancy.

Participants who stop study intervention should continue study participation while off of the study intervention, with continued evaluations as per the SoA. The reason for study intervention discontinuation should be recorded.

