## **9.2. Procedures at Visits from Day 4 through Day 28**

At each of these visits on Days 4, 6, 8, 10, 12, 14, 18, 21, 24, 28, the study staff conducting the visit will:

- Introduce themselves, explain their role to the participant, and confirm the identity of the participant
- Confirm that the means of contact is adequate to conduct the contact/visit
- Collect information on COVID-19 symptoms and signs
- Assess the Gates MRI and WHO ordinal scales
- Collect information on AEs
- Collect information on bleeding events and severity
- Collect information on concomitant medications
- Remind the participant to take the dose daily through Day 21, and not to show the study IP tablets or describe the tablets detailed appearance, to maintain the masking of the study staff.
- Collect information on adherence to study IP and any dosing error (if applicable)
- Ask participant to collect temperature, and oxygen saturation during the encounter (study staff will document temperature and oxygen saturation)
- Ask participant to collect nasal sample during the encounter for Days 4, 8, 14, 21 and 28
- Inquire about pregnancy, as appropriate.

As needed, additional contact with the study clinician or staff will be conducted at the request of the participant (e.g., if developing concerning symptoms or an AE).

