4. INTRODUCTION

The purpose of this statistical analysis plan is to describe the framework for the reporting, summarization and statistical analysis methodology of the safety and efficacy parameters measured for the Gates Medical Research Institute (MRI) study COD-01-T01-01. It is based on Protocol Gates MRI - COD-01-T01-01 Version 4, Amendment 2, 27 January 2021. This study is performed as part of an adaptive, randomized platform core protocol for treatment of early and mildly symptomatic individuals in out-patient settings with severe acute respiratory syndrome coronavirus 2 (SARS-CoV-2) infection. Additional statistical analysis plans will be developed for future protocols and interventions that will be added to the core protocol.

On January 28 and February 3, 2021, the Independent Data Monitoring Committee (IDMC) met to review the available safety and efficacy data to (1) perform the monthly safety review of accumulating data; and (2) evaluate the results of the first prespecified interim analysis for futility. Based on the review of the data, the IDMC determined on February 3, 2021, that the futility boundary was crossed and recommended that the clinical study be stopped. The final statistical analysis plan was amended to reflect changes to the planned analysis following early termination of the study.

As of February 4, 2021, the following changes were made in the study conduct:

- all randomization is ceased and no new study participants are enrolled.
- current participants must discontinue dosing of all study drug and discard their study drug.
- participants should remain in active, masked follow up and continue their study visits until Day 35 if they have had at least one dose of study drug.
 - Participants who have not reached Day 21 will continue safety follow up only until Day 35. These participants will be monitored for AEs, bleeding events and concomitant medication. These participants will not have further assessments for Gates MRI and WHO ordinal scale, symptoms, and nasal swabs for polymerase chain reaction (PCR) test.
 - Participants who have reached Day 21 but not Day 35 of study will continue safety and efficacy follow up until Day 35. These participants will be monitored for AEs, bleeding events, concomitant medication, Gates MRI and WHO ordinal scales, and symptoms. These participants will not have further nasal swabs for PCR test.
- participants who have not yet taken any study drug will discontinue the study early.

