7 STUDY POPULATIONS

7.1 Analysis Populations

An interim analysis was conducted on 28 January, 2021 using the data cut of 8 January, 2021. Efficacy interim analyses were produced based on the first 200 randomized participants who either had discontinued the study or had completed Day 28 in the ITT population. The interim efficacy primary endpoint result will be reported in the CSR using the data cut of 8 January, 2021.

IDMC's recommendation that the clinical study be stopped impacts the efficacy evaluation for the participants who were continuing in the study and had not yet reached Day 21 of the study (end of treatment period) as of 4 February, 2021. In order to have meaningful results of the final efficacy analyses, efficacy analyses will be performed on a final efficacy analysis set of participants who met either one the following criteria:

- Completed or discontinued the study or progressed prior to 5 February, 2021.
- Completed Day 21 or later visits as of 5 February, 2021.

Final analysis will be conducted following database lock.

- Efficacy analyses will be produced for randomized participants who meet the selection criteria described above and also meet the analysis population criteria described below.
- Safety analyses will be produced for all participants in the database who received at least one dose of study intervention.

Table 2: Analysis populations

| Population | Description |
|-------------------|--|
| ITT Population | All participants in the ITT population who met the criteria stated above. Participants will be analyzed according to the intervention to which they were randomized. |
| mITT population | All participants in the ITT population, who received the study intervention and have mild disease at study entry. Participants will be analyzed according to the intervention they actually received. |
| PP population | All participants in the ITT population, who received the study interventions as planned, have mild disease at study entry, and did not substantially deviate from the protocol procedures. Participants will be analyzed according to the intervention they actually received. |
| Safety population | All participants randomly assigned to study intervention, who received the study intervention. Participants will be analyzed according to the intervention they actually received. |

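### The SAP's tablet-count compliance formula is right only when 21 doses were expected; it understates compliance at every earlier stop, and exactly 100% has no reporting category

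*SAP*

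**What the plan says.** SAP 10.3 takes the tablet count at end of treatment or at discontinuation of study drug, so one rule is meant to serve completers and early stoppers alike. The rule reads: "Compliance is computed as the number expected to be taken at time of EOT or discontinuation of study drug minus number remained +1". The SAP explains the +1 by the spare tablet in the bottle and divides by the number expected. Results are to be shown in the bands "<50%, ≥50% and <75%, ≥75% and <100%, and >100% by study intervention group".

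The bottle size is in Protocol 6.8: "Each participant will receive a bottle containing twenty-two (22) tablets of active or placebo". Of these, 21 cover the planned daily doses and one is overage.

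The table covers all treated participants. SAP 10.3 states: "Treatment compliance and exposure will be summarized for the Safety population". SAP 7.1 adds: "Safety analyses will be produced for all participants in the database who received at least one dose of study intervention".

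Early stops are part of the plan and of the trial's history. Protocol 7.1 opens its list with "Study intervention will be discontinued for the following reasons". SAP section 4 records that, from 4 February 2021, "current participants must discontinue dosing of all study drug and discard their study drug".

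**The concern.** The +1 turns doses expected into tablets dispensed only if doses expected is 21. The SAP, however, ties the number expected to the time of end of treatment or discontinuation, so it falls when someone stops early while the bottle still held 22. Tablets the participant was never due to take are then subtracted as though they had been skipped.

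Negative percentages would be noticed at programming or review. Values such as 50% or 69% would not: they look like ordinary poor adherence and would be read as missed doses. Bleeding requires discontinuation (Protocol 6.4 and 7.1), and Protocol 3.2 says the drug raises bleeding risk, so the understatement could also differ between arms. That is only a possibility, because the documents give no counts of stops.

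Separately, the bands jump from below 100% to above 100%. The intended result for a completer, 21 tablets taken and one left, falls between them.

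**Working it through.** The plan gives no numerical compliance value to reproduce, so the check is direct arithmetic on its formula.

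**Inputs**
- Tablets dispensed: 22 (Protocol 6.8).
- Planned doses: 21, one daily (Protocol 6.8).
- E = doses expected by end of treatment or discontinuation; R = tablets remaining (SAP 10.3).
- Convention used here: one dose per day from Day 1, with the dose on the last dosing day d counted as expected, so E = d.

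**Formulas**
- SAP value: (E − R + 1)/E.
- Tablets taken over doses expected: (22 − R)/E.
- Shortfall: (22 − R)/E − (E − R + 1)/E = (21 − E)/E. It does not depend on R, so it applies at every level of adherence. It is zero only at E = 21.

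**Fully adherent participant.** R = 22 − d, so the SAP value is (d − (22 − d) + 1)/d = (2d − 21)/d. The true value is d/d = 100% throughout.

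| Last dosing day | SAP value | Band |
|---|---|---|
| 5 | −11/5 = −220% | <50% |
| 7 | −7/7 = −100% | <50% |
| 10 | −1/10 = −10% | <50% |
| 11 | 1/11 = 9.1% | <50% |
| 13 | 5/13 = 38.5% | <50% |
| 14 | 7/14 = 50.0% | ≥50% and <75% |
| 16 | 11/16 = 68.8% | ≥50% and <75% |
| 17 | 13/17 = 76.5% | ≥75% and <100% |
| 18 | 15/18 = 83.3% | ≥75% and <100% |
| 19 | 17/19 = 89.5% | ≥75% and <100% |
| 20 | 19/20 = 95.0% | ≥75% and <100% |
| 21 | 21/21 = 100% | none |

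**Partly adherent participant.** Last dosing day 14, two doses missed: 12 taken, R = 10. SAP value (14 − 10 + 1)/14 = 35.7%; correct value 12/14 = 85.7%. The gap is 50 points, equal to (21 − 14)/14.

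**Category gap at E = 21**
- R = 2: 20/21 = 95.2%.
- R = 1: 21/21 = 100%, no band.
- R = 0: 22/21 = 104.8%.

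More generally, a SAP value above 100% needs E − R + 1 > E, that is R = 0, an empty bottle.

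**Other readings of the sentence**
- E fixed at 21 in numerator and denominator: a full adherer scores d/21, which is 33.3% at Day 7 and 66.7% at Day 14.
- The +1 taken inside the subtraction: a perfect 21-day course scores (21 − 2)/21 = 90.5%.
- 21 in the numerator and doses due to date in the denominator: (21 − R + 1)/E = (22 − R)/E, which is correct, but the text does not say this.

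**Effect on a mean (assumed shares).** If a share s of those tabulated stopped at day d, the mean is too low by s × (21 − d)/d.
- Day 14: 5% × 0.5 = 2.5 points; 20% × 0.5 = 10 points.
- Day 7: 5% × 2 = 10 points; 20% × 2 = 40 points.

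**The case against.** The best defence is that the intent can be recovered. The remark about the spare tablet suggests the numerator was meant to be tablets taken, 21 + 1 − R, and a programmer might implement that. But the SAP uses the same expected number in both places and dates it to discontinuation. Followed as written, it gives the wrong answer. In the same way, the top band may be a slip for ≥100%; as printed it leaves the gap.

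A second argument is that the February 2021 stop may add few affected values. Those participants were told to discard their drug, those without a tablet count would have no compliance value, and SAP 9.2 bases percentages on non-missing data. This stands as a limit on size: the documents do not say how many counts exist. It does not touch stops under Protocol 7.1 or the category gap.

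Third, SAP 10.3 asks for both continuous and categorical summaries explicitly only for days of exposure, so a mean compliance is inferred from the general conventions in SAP 9.2. The mean shifts are therefore illustrations and should carry little weight.

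Fourth, the boundary of the negative range depends on the day convention: if the dose on the stop day is not counted as expected, it runs through Day 11 instead of Day 10.

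Finally, this is one descriptive summary. Days of exposure, in the same section, are unaffected, and adherence is also recorded at visits (Protocol 9.2). All of that is correct and limits the importance, not the error.

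**Conclusion.** The concern holds. As written, the formula is correct only when 21 doses were expected and understates compliance by (21 − E)/E at every earlier stop. For a participant who missed nothing, the value is negative through Day 10, below 50% through Day 13, in the second band on Days 14 to 16, and in the third on Days 17 to 20. The error is small late in treatment, 17 points at Day 18 falling to 5 at Day 20. At Day 21 the correct value of 100% belongs to no band.

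These results rest on the 22-tablet bottle, one dose per day from Day 1, and the last dosing day counted as expected. How many participants are affected cannot be determined from the documents. The consequence is confined to the compliance summary in the Safety population; the documents tie no efficacy test, futility decision or per-protocol rule to it. It should be corrected because the rule gives wrong results when followed and the correction is nearly free. SAP Version 2.0 was issued after the study stop, and its change list does not mention compliance.

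**What to change.** Replace the formula in SAP 10.3 with: compliance = (22 − tablets remaining) / (doses scheduled from first dose to end of treatment or discontinuation) × 100. State whether the dose on the day of discontinuation counts as scheduled. This gives 100% for a fully adherent participant at every stop day and matches the present formula at 21 doses.

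Make the last category ≥100%. If it is useful to keep perfect adherence apart from use of the spare tablet, show exactly 100% and above 100% as two categories.

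Add a rule for tablets discarded without a count after 4 February 2021: use the adherence recorded at visits where it yields a dose count, and otherwise report compliance as missing.

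The cost is SAP wording and one line of programming for the formula, with no new data for participants who have a tablet count. The fallback draws on a second data source and needs a little more work; the documents do not show whether the visit records give dose counts.

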11 EFFICACY PARAMETERS

The primary efficacy endpoint is the proportion of participants who progress to moderate or severe disease category or higher (Gates MRI ordinal scale ≥ 3) at any day through Day 28.

Secondary efficacy endpoints include:

- Time to disease resolution, defined as symptoms resolution only (new onset COVID-19 symptoms resolved, and pre-existing symptoms returned to baseline) through Day 28
- Time to disease resolution, defined as both viral clearance (two consecutive negative diagnostic tests) and symptoms resolution (new onset COVID-19 symptoms resolved, and pre-existing symptoms returned to baseline*) through Day 28
- Proportion of participants who progress to moderate or severe disease category or higher (Gates MRI ordinal scale ≥ 3) at Days 8, 14, and 21
- Proportion of participants who achieve disease resolution, defined as symptoms resolution only, at Days 8, 14, 21 and 28
- Proportion of participants who achieve disease resolution, defined as both viral clearance and symptoms clearance, at Days 8, 14, 21 and 28
- Gates MRI scale score at Days 8, 14, 21, and 28
- WHO ordinal scale score at Days 8, 14, 21, and 28
- Incidence of hospitalization through Days 8, 14, 21, and 28
- Number of days of hospitalization through Days 8, 14, 21, and 28

Exploratory endpoints include:

- Quantity (and change from baseline) of SARS-CoV-2 virus at Days 8, 14, 21 and 28
- Phylogenetic relationships of SARS-CoV-2 viruses sequenced from positive nasal swab samples

11.1 Primary Analysis

11.1.1 Estimand

The treatment policy estimand with respect to the primary efficacy objective is defined by the following:

Population: Participants in the ITT population.

Patient-level outcome: Binary outcome of progression to moderate or severe disease category or higher (Gates MRI ordinal scale ≥ 3) at any day through Day 28.

Intercurrent events: The following intercurrent events to be taken into account:

1. If a death occurs on or prior to Day 28, the participant will be considered as having progression to moderate or severe category (Gates MRI ordinal scale ≥ 3) through Day 28.
2. If hospitalization occurs on or prior to Day 28, the participant will be considered as having progression to moderate or severe category (Gates MRI ordinal scale ≥ 3) through Day 28.
3. If a participant is lost to follow-up on or prior to Day 28, the last observed Gates MRI ordinal scale status evaluation will be carried forward onward to Day 28.
4. If a participant discontinues the study prior to initiation of IP dosing on Day 1 (for any reason: lost to follow-up, progression to moderate or severe COVID-19, withdrawal of consent) and no Gates MRI ordinal scale assessment is available, the participant will be considered as having progression to moderate or severe category (Gates MRI ordinal scale ≥ 3) through Day 28.

Participants who discontinue study intervention will be followed at least until end of study, Day 35.

Population-level summary measure: Proportion of participants who progress to moderate or severe disease category or higher (Gates MRI ordinal scale ≥ 3) at any day through Day 28.

The primary efficacy analysis will be conducted in the ITT population. Participants randomized to rivaroxaban will be compared to participants randomized to placebo. For the primary efficacy analysis, the following primary hypothesis will be tested: Prophylactic treatment with rivaroxaban will reduce progression to moderate or severe disease category or greater (Gates MRI ordinal scale ≥ 3) relative to placebo in high risk participants with mild COVID-19.

The proportion of participants who have progression of COVID-19 at any time up to and including Day 28 and the corresponding 2-sided 95% CI, computed using the Mid-p method, will be summarized for the study intervention and control. The absolute difference in the risk of progression of COVID-19 and the corresponding 2-sided 95% CI will be assessed using the

stratified Miettinen and Nurminen method [Miettinen, 1985] with the Cochran-Mantel-Haenszel (CMH) weights [Lu, 2008], stratified by number of days since onset of symptoms at time of randomization (<6 days or ≥6 days). The point estimates and variance estimated for each stratum j using the Miettinen and Nurminen method are defined as

$$\hat{d}_j = \hat{p}_{1j} - \hat{p}_{2j}$$

where \hat{p}_{1j} and \hat{p}_{2j} are the proportions of participants in rivaroxaban and placebo group who had progression of COVID-19 through Day 28, respectively, and

$$\widetilde{Var}_j(\delta) = \left(\frac{n_j}{n_j - 1}\right) \left(\frac{\tilde{p}_{1j}(\delta) (1 - \tilde{p}_{1j}(\delta))}{n_{1j}} + \frac{\tilde{p}_{2j}(\delta) (1 - \tilde{p}_{2j}(\delta))}{n_{2j}} \right)$$

where $n_j = n_{1j} + n_{2j}$, and $\tilde{p}_{1j}(\delta)$ and $\tilde{p}_{2j}(\delta)$ are the maximum likelihood estimates of rivaroxaban and placebo proportions under the restriction that the risk difference is δ . For the hypothesis specified, $\delta = 0$. The maximum likelihood estimates of p_{1j} and p_{2j} , subject to the constraint that the risk difference is δ , are computed as

$$\tilde{p}_{1j}(\delta) = 2u \cos(w) - b/3a \quad \text{and} \quad \tilde{p}_{2j}(\delta) = \tilde{p}_{1j}(\delta) + \delta$$

where

$$\begin{aligned} w &= (\pi + \cos^{-1}(v/u^3))/3 \\ u &= \text{sign}(v) \sqrt{b^2/(3a)^2 - c/3a} \\ v &= b^3/(3a)^3 - bc/6a^2 + d/2a \\ a &= 1 + \theta \\ b &= -(1 + \theta + \hat{p}_{1j} + \theta\hat{p}_{2j} + \delta(\theta + 2)) \\ c &= \delta^2 + \delta(2\hat{p}_{1j} + \theta + 1) + \hat{p}_{1j} + \theta\hat{p}_{2j} \\ d &= -\hat{p}_{1j}\delta(1 + \delta) \\ \theta &= n_{2j}/n_{1j} \end{aligned}$$

The CMH weights will be used to combine the point estimates and variance estimates that are calculated within each stratum using the Miettinen and Nurminen method.

$$\hat{d} = \sum_j w_j \hat{d}_j$$

$$\widetilde{Var}(\delta) = \sum_j w_j^2 \widetilde{Var}_j(\delta)$$

where CMH weights, w_j , are defined as

$$w_j = W_j / \sum_k W_k$$

where

$$W_j = \left(\frac{1}{n_{1j}} + \frac{1}{n_{2j}} \right)^{-1}$$

A score-based test statistic for the null hypothesis is that the risk difference equals δ can be expressed as

$$Z(\delta) = (\hat{d} - \delta) / \sqrt{\widehat{var}(\delta)}$$

The 95% confidence interval for the risk difference consists of all values of δ for which the score test statistic $Z(\hat{\delta}_L) = z_{1-\alpha/2}$ and $Z(\hat{\delta}_U) = -z_{1-\alpha/2}$, where $z_{1-\alpha/2}$ is the $(1 - \alpha/2)$ percentile of the standard normal distribution, and $\hat{\delta}_L$ denotes the lower limit and $\hat{\delta}_U$ denotes the upper limit.

For participants who are lost to follow-up prior to Day 28, the last disease status evaluation will be used as last observation carried forward to Day 28 to address the missing visit data in the primary analysis.

